The Run-In Period: Following successful screening, all subjects (CSII, MDI or SAP) will enter the run-in period and collect blinded CGM data while using their own diabetes therapy. Blinded CGM consists of using a Guardian Sensor (3) connected to a Guardian Link (3) transmitter. A total period of 2 weeks of CGM data will be collected.

Cohort 1: CSII

The Study Period: After completion of the run-in period, subjects with CSII therapy (minimum N= 280) will be randomized and placed into one of 2 different arms during the study period:

1. The HCL Arm will use the MiniMed system (i.e., using Auto Mode) for 6 months during the study

CEP304 Clinical				
CEP304DOC	Revision	Н	Page 55 of 182	Medtronic

period. There will be N=140 for the HCL arm.

- 2. The Control Arm will use the MiniMed Pump without CGM.
 - a) Blinded CGM (Guardian Link (3) Transmitter and Guardian Sensor (3)) will only be worn at baseline, 3 months, and 6 months (two weeks of sensors use). There will be N=140.

Cohort 2: MDI

The Study Period: After completion of the run-in period, subjects with MDI therapy (minimum of N=280) will be randomized and placed into one of 2 different arms during the study period:

- 1. The HCL Arm will use the MiniMed system (i.e., using Auto Mode) for 6 months during the study period. There will be N=140 for the HCL arm.
- 2. The Control Arm will be using their current insulin therapy (MDI)

The Multiple Daily Injection (MDI) subjects will remain on MDI therapy with subjects using their own insulin for 6 months during the study period. The Sponsor will not provide insulin. Blinded CGM (Guardian Link (3) Transmitter and Guardian Sensor (3)) will only be worn at baseline, 3 months, and 6 months (two weeks of sensors use). There will be N=140.

MDI subjects who are currently using CGM, i.e. Dexcom or Medtronic Guardian Connect or who are currently using a SMBG alternative, i.e. Libre, will be allowed to enroll in the study and continue using their own device. There will be N=100

Cohort 3: SAP

[figure not shown]
The Study Period: After completion of the run-in period, subjects with SAP therapy (minimum N= 280) will be randomized and placed into one of 2 different arms during the study period. Sensor insertion placement will be according to User guide:

- 1. The HCL Arm will use the MiniMed system (i.e., using Auto Mode) for 6 months during the study period. There will be N=140 for the HCL arm.
- 2. The Control Arm will be using SAP therapy using the MiniMed System.

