- o Approximately 30 minutes to 2 hours after the Guardian Sensor (3) is initialized, the Study Pump will alert the user to enter meter BGs to perform initial calibration.
- After the first calibration, the user must calibrate the Guardian Sensor (3) with the study meter within 6 hours of the first calibration.
- o The user must calibrate with the study meter when prompted by the study pump via the Smart Cal feature
- o The user must calibrate with the study meter every 12 hours after last calibration.
- Recommend 3-4 calibrations per day with the study meter
- o All BGs used for Auto Mode in the MiniMed Pump system can also be used for sensor calibration. However, calibrating during rapid changes (2 or 3 arrows) may temporarily decrease sensor accuracy. Best practices should be followed for each BG measurement

CEP304 Clinical I				
CEP304DOC	Revision	Н	Page 88 of 182	Medtronic

(e.g. clean hands, accepting the calibration on the pump without delay)

- Other recommendations:
 - Always have clean dry fingers when you check your blood glucose
 - Only use your fingertips to obtain blood samples for calibration

Auto Mode Settings:

- The Auto Mode (Closed Loop) target for the closed loop algorithm is set at 120 mg/dL (6.7 mmol/L).
- o The Temp target setting in the pump may be used when subject exercises. Temp Target Threshold is set to 150 mg/dL (8.3 mmol/L).
- Alarms that are fixed into system:
 - SG at or below 50 mg/dL (2.8 mmol/L)
 - When SG at or above 300 mg/dL (16.7 mmol/L) for one hour
 - When SG at or above 250 mg/dL (13.9 mmol/L) for 3 hours
- High Setup limit (i.e. the setting for a high glucose alert threshold based on sensor reading) is recommended to be set at 300 mg/dL (16.6 mmol/L)
 - Alert setting options may be set per investigator discretion
- Low Setup limit (i.e. the setting for a low glucose alert threshold based on sensor reading) is recommended to be set at 70 mg/dL (4.0 mmol/L)
 - Alert setting options may be set per investigator discretion
 - For subjects 2-6 years of age, low limit should be set to 80mg/dL (4.4mmol/L) and no lower than 70mg/dL(4.0 mmol/L)
 - Subjects will be instructed to follow up with an SMBG confirmatory measurement when receiving a low alert
- Insulin carbohydrate ratios may be adjusted throughout study.
- Active insulin time may also be adjusted.

CEP304 Clinical Inv				
CEP304DOC	Revision	Н	Page 89 of 182	Medtronic

Manual Mode Settings:

- o High Set up Limit recommend to be set at 300 mg/dL (16.6 mmol/L)

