related to a failure of the device or deterioration in its effectiveness, or any inadequacy in its labeling or directions for use leading to death or serious deterioration in a subject's health within 72 hours after the occurrence (Canada Medical Device Regulations, SOR/98-282; 77, 59.)

For Europe, Australia and New Zealand: It is the responsibility of the investigator to follow their IRB/EC reporting requirements.

For Australia: It is the responsibility of the investigator are to report USDAE to their HREC and institution without undue delay and no later than 72 hours of the Principal Investigator becoming aware of the event.

(NHMRC Safety monitoring and reporting in clinical trials involving therapeutic goods November 2016 section C.2.g)

For US, Canada, Europe, Australia and New Zealand:

The Sponsor will complete safety and vigilance reporting and notify the investigator and IRB/EC of any event that results in a safety report to the regulatory authorities. Documentation of IRB/EC notification of any safety event must be kept at the investigational center and a copy sent to the Sponsor.

Reporting of Glycemic Events

- 1. **Severe Hypoglycemia** is an event requiring assistance of another person due to altered consciousness to actively administer carbohydrate, glucagon, or other resuscitative actions. This means that the subject was impaired cognitively to the point that he/she was unable to treat his or her self, was unable to verbalize his or her needs, and was incoherent, disoriented and/or combative.
 - These episodes may be associated with sufficient neuroglycopenia to induce seizure or coma. Plasma glucose measurements may not be available during such an event, but neurological recovery attributable to the restoration of plasma glucose to normal is considered sufficient evidence that the event was induced by a low plasma glucose concentration. (Adapted from American Diabetes Association Workgroup on Hypoglycemia, Diabetes Care 28:1245-1249, 2005)
- Severe Hyperglycemia is defined as Hyperglycemia (blood glucose >300 mg/dL (16.7mmol/L)) with blood glucose ketones >1.5mmol/L, urine ketones moderate or large, or accompanied by symptoms of nausea, vomiting or abdominal pain.

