device deficiencies that are reported to the TS will be documented by the TS staff.

Medtronic will review all device deficiencies and determine whether the deficiency requires reporting to regulatory agencies; vigilance reporting includes all devices that are CE marked in Europe. The sponsor will ensure timely Device Deficiency reporting to meet regulatory requirements.

Note: For commercially available devices, device deficiency reporting will be documented per study and relevant regulatory requirements

Depending on the country, the investigational center will be provided with a copy of all TS calls for their subjects. The TS calls should be reviewed for investigational center staff awareness and for the possibility of an AE. If an AE is detected the investigational center staff will also complete an AE eCRF.

In the US, all device deficiencies reported directly to the investigational center staff by a subject should either be reported to the TS by the subject or investigational center staff.

In Europe Canada, Australia and New Zeland all device deficiencies reported directly to the investigational center staff by a subject and should be documented on a Device Deficiency eCRF.

A device deficiency is any communication that alleges inadequacy of a medical device with respect to its identity, quality, durability, reliability, safety, or performance. NOTE: Device deficiencies include malfunctions, use errors, and inadequate labeling. (Adapted from ISO14155:2011 3.15)

In the US, Canada, Europe, Australia and New Zealand: While 24-Hour TS may direct the return/replacement of study devices, all such transactions will be managed by investigational centers directly. Subjects are asked to call the 24-Hour TS for help with the troubleshooting of devices.

It is the responsibility of the Investigator to follow the center's IRB/EC and local regulatory authority reporting requirements.

For Europe Canada, Australia and New Zealand:

Device deficiencies that did not lead to an Adverse Event, but could have led to an SADE require immediate reporting to the sponsor via completion of the applicable CRF. In addition, follow the IRB/EC and regulatory authority reporting requirements per ISO14155:2011 if any of the following apply:

- a) if either suitable action had not been taken,
- b) if intervention had not been made, or
- c) if circumstances had been less fortunate

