7.10 Safety Evaluation

The primary safety endpoint is the event rate of severe hypoglycemia and DKA from both Groups (1 & 2) during the first 6 months of study phase and second 6 months of continuation phase. The descriptive summary statistics will be presented by number of event and event rate (100 patient years) for severe hypoglycemia and DKA **separately**.

The safety of the study will be evaluated and summarized per arm, including but not limited to the following:

• Diabetic ketoacidosis (DKA)

CEP304 Statistical Analysis Plan Revision 3.0 Page 34 of 34 Medtronic

- Severe hypoglycemia
- Severe hyperglycemia
- Serious adverse events (SAEs)
- Unanticipated adverse device effects (UADEs)

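### For CSII and non-CGM MDI controls, the per-arm severe hyperglycemia summary mixes detection with harm where events are asymptomatic and ketone-only

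*Protocol*

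**What the plan says.** **Definition.** Protocol 17.2, Reporting of Glycemic Events, sets the event as follows: "Severe Hyperglycemia is defined as Hyperglycemia (blood glucose >300 mg/dL (16.7mmol/L)) with blood glucose ketones >1.5mmol/L", with the alternatives "urine ketones moderate or large, or accompanied by symptoms of nausea, vomiting or abdominal pain". Whichever second criterion applies, a blood glucose above 300 mg/dL is needed. For severe hypoglycemia the same section accepts that "Plasma glucose measurements may not be available during such an event"; severe hyperglycemia has no such allowance.

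**HCL arm.** Protocol 10.1, Auto Mode Settings, lists two fixed high alarms: "When SG at or above 300 mg/dL (16.7 mmol/L) for one hour" and "When SG at or above 250 mg/dL (13.9 mmol/L) for 3 hours". Under Protocol 17.2 sites obtain source documents, including device uploads, and review source documents for further adverse events. For this arm the uploads contain sensor glucose.

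**Controls.** For the CSII cohort, Protocol section 6 states: "The Control Arm will use the MiniMed Pump without CGM". Flash monitoring is not permitted for that cohort during the study. MDI subjects who already use a CGM or flash device may keep it (N=100). Protocol 19.1.4 instead describes equal MDI numbers with and without CGM. The other MDI controls wear only blinded sensors, at baseline and months 3 and 6. All subjects are told to test 4-6 times a day (Protocol 14.1).

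**Use of the event.** SAP 7.10 states "The safety of the study will be evaluated and summarized per arm", and severe hyperglycemia is on the list that follows. Under Protocol 18.2 its rate goes to the DMC.

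**The concern.** The two arms do not look for this event in the same way. An HCL subject with a prolonged high sensor reading gets an alarm and leaves a trace. A control without real-time CGM finds the same excursion only if a routine fingerstick falls inside it or symptoms prompt a test. An asymptomatic ketotic excursion between tests goes unrecorded in that control.

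The per-arm rates are then partly a comparison of monitoring. A higher HCL rate could be read as device harm when it is better detection, or a real reduction in events could be hidden. Table 16 makes this a numerically important event in children: its reference rate for ages under 15 is 71.64 per 100 patient-years, against at most 9.9 for DKA and 10.2 for severe hypoglycemia in the same column.

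The text available contains no common trigger for glucose or ketone testing and no caution about reading the rates between arms. The Clinical Events Committee reviews reported events, so it cannot recover unreported ones.

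**Working it through.** The plan states no figure on this point, so there is nothing to reproduce. What follows shows scale only.

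**1. Who is affected.** All 140 CSII controls. With N=100 MDI subjects on their own device and 1:1 allocation, 50 of 140 MDI controls have one and 90 do not. With the equal split of Protocol 19.1.4, 70 do not. Affected controls: 140 + 70 to 140 + 90 = 210-230 of 420, or 50-55%.

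**2. Chance that a routine fingerstick falls inside an excursion.** Assumptions: random onset over 24 hours, and k tests evenly spaced over 16 waking hours. That gives k − 1 gaps of 16/(k − 1) hours and one overnight gap of 8 hours. For an excursion lasting d hours:

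P = 1 − Σ max(0, gap − d)/24

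For k = 4 and d = 4: gaps of 5.33, 5.33, 5.33 and 8, so P = 1 − (3 × 1.33 + 4)/24 = 0.67. If every excursion is found in the HCL arm and true harm is equal, the apparent rate ratio is 1/P.

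| d (hours) | P, 4 tests | P, 6 tests | 1/P |
|---|---|---|---|
| 2 | 0.33 | 0.50 | 3.0-2.0 |
| 3 | 0.50 | 0.75 | 2.0-1.33 |
| 4 | 0.67 | 0.83 | 1.5-1.2 |
| 6 | 0.92 | 0.92 | 1.09 |
| 8 | 1.00 | 1.00 | 1.0 |

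The result depends almost wholly on d, which the documents do not give.

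**3. Events.** Patient-years per arm per cohort: 140 × 0.5 = 70. At 71.64 per 100 patient-years this is 50.1 events. That rate is for under-15s only; Table 16 gives none for older subjects, so the counts are a scale and not a forecast.

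**4. An assumed 30% miss in non-CGM controls**, with own-device MDI controls counted as fully detected. Intervals use exp(log RR ± 1.96 × √(1/e₁ + 1/e₀)).
- CSII alone: 50.1 against 0.70 × 50.1 = 35.1; ratio 1.43 (0.93-2.20).
- MDI controls, 70 without CGM: 50.1 × (70 × 0.70 + 70)/140 = 42.6. Both cohorts: 100.3 against 77.7; ratio 1.29 (0.96-1.74).
- MDI controls, 90 without CGM: 50.1 × (90 × 0.70 + 50)/140 = 40.5. Both cohorts: 100.3 against 75.6; ratio 1.33 (0.98-1.79).

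**5. Half of events symptomatic and found in both arms.** The miss over all events falls to 15%. Control totals become about 89.0 (70 without CGM) or 87.9 (90 without CGM), giving ratios of 1.13 and 1.14, with intervals within 0.85-1.52.

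**6. Visits do not explain the gap.** From Visit 4 to Visit 9 there are 12 scheduled contacts in the HCL arm and 11 for CSII and MDI controls, and adverse events are elicited at each one. The asymmetry lies in home monitoring.

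**The case against.** - **The summary is descriptive and not primary.** Severe hyperglycemia is in neither the primary safety endpoint nor the success criteria, which concern severe hypoglycemia and DKA. The explicit HCL-versus-control description in SAP 7.9 also covers only those two events. This stands and limits the consequence, but readers will still compare a per-arm table by arm.
- **Symptomatic events need no alarm.** This stands. Differential detection falls mainly on ketone-only events.
- **The direction is not fixed.** An alarm may prompt earlier correction and prevent a true event. A sensor alarm is also not a blood glucose or ketone value, and the written instruction to confirm by fingerstick covers low alerts only. The step from high alarm to recorded event is an inference. Both points stand.
- **The DMC has context.** Its reference rate is external, it weighs device malfunction against non-compliance and infusion-set problems, and it is told to treat the thresholds with caution. This helps with single events and external comparison, but does not correct a between-arm reading of the rate.
- **Parts of both documents are blacked out**, including the text of Protocol 5.3 and SAP text before 7.10. A sensor-based hyperglycemia summary may already be there, so the fix is conditional on that.

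A reader might infer that the plan would yield a statistically clear false signal against HCL: a 30% miss in every CSII and MDI control gives 100 against 70 events, ratio 1.43 (1.05-1.94). The documents do not support that. It ignores MDI controls who keep their own device, removes symptomatic events that would be found anyway, and applies an under-15 rate to cohorts aged up to 80.

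**Conclusion.** The point holds in a limited form. In the 6-month study period, asymptomatic ketone-only severe hyperglycemia is more likely to be found in the HCL arm than in CSII controls or MDI controls without their own CGM. The per-arm summary in SAP 7.10, and any between-arm reading of the DMC rate, therefore mixes detection with harm.

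Detection alone would raise the HCL rate. The documents fix neither the net direction nor the size. The illustrative ratios of 1.29-1.33, or 1.13-1.14 with half of events symptomatic, rest on an assumed 30% miss, full detection in the HCL arm and among own-device MDI controls, and a borrowed paediatric rate. All of those intervals include 1. It would be wrong to call the contrast biased against HCL by a known amount.

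The sensor-augmented pump cohort, MDI controls with their own CGM, the continuation period (all subjects on HCL) and the primary safety endpoint with its success criteria are largely unaffected. This is a worthwhile reporting improvement and does not threaten the main conclusions.

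**What to change.** In SAP 7.10, for the 6-month study period in the CSII and MDI cohorts, with MDI also split by own-CGM use:

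1. Report severe hyperglycemia per arm in two rows: (a) events with symptoms or treated in a health care facility, and (b) asymptomatic events that qualify on ketones alone. Flag (b) as not comparable between arms.
2. Unless the blacked-out text already has it, add the per-arm rate of episodes with sensor glucose at or above 300 mg/dL for at least one hour in the month-3 and month-6 CGM fortnights. The plan already uses these windows for its sensor-based arm comparisons.
3. Give the DMC the same split.

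The cost is SAP wording and one extra table, with no new procedures. Protocol 10.7.1 has sites record treatment and a description of each event; whether the form captures which criterion was met should be checked, since otherwise row (b) must be taken from the narratives.

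There are downsides. Row (a) has fewer events and a wider interval, and symptoms are self-reported under unmasked treatment. The sensor measure covers 28 of about 180 days and counts high glucose without ketosis, so it supplements the event rate and does not replace it.

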18.1 Clinical Events Committee

A clinical events committee (CEC) consisting of external physicians with an expertise in Endocrinology and

CEP304 Clinical				
CEP304DOC	Revision	Н	Page 130 of 182	Medtronic

the management of diabetes including Insulin Pumps and CGM will be convened. The CEC will review all reports of:

- Serious Adverse Event
- Serious Adverse Device Effect
- Unanticipated Adverse Device Effect
- Severe Hypoglycemia
- Diabetic Ketoacidosis
- Severe Hyperglycemia

The CEC will assess events to determine agreement or disagreement with the investigator classification of an event. The CEC will only provide three causality assessments for device and procedure relatedness: Not Related, Possible, and Causal relationship.

Causality Categories for Investigational Center	Causality Categories for CEC:
Not Related	Not Related
 Unlikely 	• Possible
 Possible 	Causal relationship
 Probable 	
Causal relationship	

18.2 Data Monitoring Committee

A Data Monitoring Committee (DMC) consisting of external physicians with an expertise in Endocrinology and the management of insulin requiring diabetes including CGM, along with an external statistician will be convened to review study progress and safety. The Board will convene approximately every 90 days, until at least 2000 Auto Mode patient days in both the 2-6 year and 7-13 year age groups in the CEP302 and/or CEP304 study have been reviewed and approved by the DMC. After review of the patient day report(s), the

CEP304 Clinical I				
CEP304DOC	Revision	Н	Page 131 of 182	Medtronic

meeting cadence will transition to 180 days. The Board will also meet when ad hoc review is required.

In addition, the DMC will review interim analysis data, performed by an independent statistician, per Cohort at the following points in time:

- After 80 subjects from Group 1 (baseline A1c > 8%) have completed the first 6 months of the study period
- After 80 subjects from Group 2 (baseline A1c ≤ 8%) have completed the first 6 months of the study period

The DMC will perform 4 main functions:

First: DMC will review data related to staged enrollment of subjects 2-6years of age (Ad Hoc Review)

- Subjects 2-6 years of age will be allowed to enroll in the post approval study, once DMC has reviewed
 data from 10 subjects age 2-4 years who have completed participation in the study period of the
 CEP302 study and has given approval to enroll
- Should an Unanticipated Severe Hyperglycemia event which meets SAE criteria or a device related Severe Hypoglycemia event occur, subjects 2-6 of age will not be allowed to enroll, unless FDA provides approval to include this age group.

Second: DMC will track and trend the overall Safety of the study.

Event rate, defined as number of events per 100 patient years will be reviewed by the DMC with respect to the following:

- Event rate of all SAEs.
- Event rate of severe hypoglycemia
- Event rate of severe hyperglycemia
- Event rate of DKA
- Event rate of device related adverse events.

Applicable information for device related adverse events may include:

- Whether or not the event was unanticipated
- Review of sensor data from CareLink report (when applicable)
- Review of pump data from CareLink report (when applicable)
- Misuse of the device by the user

CEP304 Clinical Inv				
CEP304DOC	Revision	Н	Page 132 of 182	Medtronic

Third: Based on their meetings, DMC will recommend a decision to the sponsor regarding the following:

- Whether or not enrollment should be halted.
- Whether or not the entire study will need to be stopped including for those subjects who have received study devices already.

Fourth: During Interim analysis, independent statistician will perform sample size re-estimation and report it to DMC. DMC will then provide a recommendation:

- Whether or not N of enrollment per Group should be increased
- Whether or not the entire study will need to be stopped for futility

General guidance for DMC's recommendations to sponsor should be based on the following:

In general, a DMC recommendation regarding study stoppage or resumption of enrollment should be made to the sponsor within 1 week of the DMC meeting where the determination is made. However, if more data is needed, the DMC may meet again to re-assess their decision within 2 weeks or when required data becomes available.

Review of events may require the following information. Final disposition may be delayed based on obtaining this information:

- Monitoring by sponsor at site
- Device return and failure analysis
- CareLink upload and review of CareLink reports
- Subject clarification to site regarding details about the event
- Source documents that support event: Paramedic records; ER records; Lab records; Hospital admission and discharge summary

The following factors should be carefully considered in the DMC's recommendation to sponsor:

- 1. Was the severe hypoglycemia or DKA related to the HCL algorithm, or was it related to a known insulin pump risk? For example, a question that may be considered in DKA would be whether the event was related to an infusion set issue or caused by the HCL algorithm.
- 2. Another important consideration would be if the severe hypoglycemia, severe hyperglycemia or DKA event was related to a device malfunction versus patient non-compliance. For example, if a software anomaly leading to an under-delivery of insulin is discovered versus the subject repeatedly ignoring alarms prompting the subject to take action.

CEP304 Clinical				
CEP304DOC	Revision	Н	Page 133 of 182	Medtronic

- 3. Severe hypoglycemia, severe hyperglycemia or DKA caused directly by an infusion set issue when the study pump is functioning as intended would likely result in acceptance to proceed with the study versus severe hypoglycemia or DKA that are directly caused by the HCL algorithm or a device malfunction might stop study enrollment or entire study altogether.
- 4. It should be noted that the final determination of causality related to HCL System that is made by the DMC may include additional factors which the members consider to be clinically relevant and important.
- 5. The DMC may take into account the thresholds listed below for the number of subjects experiencing hypoglycemia requiring assistance from another person or DKA to identify when the number of subjects experiencing these events exceeds the number that would be anticipated for the study population over the duration of this study. These thresholds should be interpreted with caution due to potential differences in study populations and study design.
 - a. Rates taken from Type 1 exchange (Cengiz et. Al, and Weinstock et. Al), are higher than the clinical studies STAR 3, 530G adult in-home study (CEP266) and 530G Pediatric in-home study(CEP287).
 - b. Reasons for lower rates of severe hypoglycemia and DKA in the clinical studies mentioned could be related to several factors including but not limited to the exclusion of those with DKA or severe hypoglycemia, additional attention secondary to mandatory study visits, selection bias of motivated patients willing to perform study procedures and access to free study devices during the course of the study.
 - c. The CL outcome study (CEP304) will include several aspects noted above including the provision of free study devices during the course of the study. Therefore, the DMC should consider stopping study if rates of severe hypoglycemia and DKA are significantly worse (e.g. higher) in HCL arm than rates provided by clinical trials mentioned in Table 16.
 - d. Age consideration may also be factored in by the DMC. For example, severe hypoglycemia rates in those >25 years may be higher than those 25 years and below.
 - e. Should DKA and/or severe hypoglycemia occur early in the study, the DMC should consider that the higher event rate may not necessarily represent a significant safety concern.

CEP304 Clinical Investigation Plan

CEP304DOC Version H Page 134 of 182 **Medtronic**

Table 16. Hyperglycemia/Hypoglycemia / DKA Threshold

Adverse Event	Reference	Reference Rate > 25 years old	Reference Rate 15-25 years old	Reference Rate <15 years old
Severe Hyperglycemia events per 100 patient years	CER 302	NA	NA	71.64
DKA events per 100 patient years	STAR 3 Bergenstal et. al	SAP arm: 0.68 Control arm: 0	SAP arm: 2.7 Control arm: 3.6	SAP arm: 2.2 Control arm: 0
	530 G Adult inhome study CEP 266 (MDT on file)	1.27	3.4	N/A
	530 G Pediatric inhome study CEP 287 (MDT on file)	N/A	N/A	0
	Type 1 exchange Weinstock et. al	4.8	N/A	N/A
	Type 1 exchange Cengiz et. al	N/A	9.9	9.9
Severe hypoglycemia per 100 patient years	STAR 3 Bergenstal et. al	SAP arm: 16.5 Control arm: 20.9	SAP arm: 5.4 Control arm: 3.9	SAP arm: 10.2 Control arm: 3.6
	530 G Adult inhome study CEP 266	0.85	0	N/A

CEP304 Clinical Investigation Plan

CEP304DOC Version H Page 135 of 182 **Medtronic**

Adverse Event	Reference	Reference Rate > 25 years old	Reference Rate 15-25 years old	Reference Rate <15 years old
	(MDT on file)			
	530 G Pediatric inhome study CEP 287 (MDT on file)	N/A	N/A	1.42
	Type 1 exchange Weinstock et.	11.8	N/A	N/A
	Type 1 exchange Cengiz et. al	N/A	6.2	6.2

CEP304 Clinical I				
CEP304DOC	Revision	Н	Page 136 of 182	Medtronic

Descriptive summary (i.e. not statistically powered) for severe hypoglycemia and DKA events rates will be performed between the HCL and control arms for each age group (< 15 years, 15-25 years, and > 25 years), as well as the overall event rates.

Severe hypoglycemia and DKA event rates were taken from the following:

- 1. Richard Bergenstal et.al: Effectiveness of Sensor-Augmented Insulin-Pump Therapy in Type 1Diabetes.New England Journal of Medicine, 2010; 363:311-20
- 2. Weinstock et. al: Severe hypoglycemia and diabetic ketoacidosis in adults with type 1 diabetes: results from the T1D Exchange clinic registry. J Clin Endocrinol Metab. 2013 Aug;98(8):3411-9.
- 3. Cengiz et. al: Severe hypoglycemia and diabetic ketoacidosis among youth with type 1 diabetes in the T1D Exchange clinic registry. Pediatr Diabetes. 2013 Sep;14(6):447-54.
- 4. MDT on file: Statistical Analysis Plan (SAP) for CEP304, 056-F286

19. Statistical Design and Methods

